#### **4.2 Health Technologies being assessed**

The diagnostic tool/management decision aid will be designed using statistical models that combine variables describing results of the index tests: age, physical examination of the lower abdomen including digital rectal examination (DRE) of the prostate, symptom score from questionnaire, micturition frequency and volume from a voiding diary, urine flow rate and voided volume and post void residual urine volume, to accurately predict the urodynamic diagnosis separately defined by the reference standard of urodynamics. The index tests are all in routine use for this condition within either primary or secondary NHS care and do not involve any physical risk to participants.

Urodynamics, the reference test, is routinely performed in secondary care and involves measurement of bladder pressure during bladder filling and whilst passing urine (voiding) by a thin catheter passed through the urethra into the bladder and rectum. It gives diagnoses of detrusor overactivity during filling and bladder outlet obstruction or detrusor underactivity during voiding. If the test shows none of these diagnoses, then the result is 'normal urodynamics'. The test involves mild to moderate discomfort and risks causing urinary tract infection which occurs in 5% of subjects [5].

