## **6 Study Design and Setting**

### **6.1 Design**

We plan a prospective diagnostic accuracy study to determine which of a number of simple clinical variables (index tests) collected in primary care and used individually or in combination best predict urodynamic diagnosis in men who present to their GP with lower urinary tract symptoms (LUTS). Two cohorts of participants will undergo the series of simple index tests and the invasive reference test (urodynamics) in community settings. We aim to recruit 880 men from primary care to the study.

The study will follow the NICE pathway for LUTS as standard (<http://www.nice.org.uk/guidance/cg97>) [1]. Study participants will undergo standard assessment recommended for primary care by NICE. In addition, urine flow rate and residual urine estimation (optional in the NICE pathway and not routine in primary care) will be included. All men in the study will undergo urodynamics as the reference test for diagnostic accuracy; this is a specialist test in the NICE pathway. All results will be given to the GP with the likely diagnosis and recommended management options to decide on further care.

Test variables collected from the first cohort will be used to develop a statistical model which will combine results from the index tests to best predict urodynamic diagnosis from the reference test. The diagnostic accuracy of the model will then be ascertained using the results from the second cohort. A qualitative study will explore the feasibility of creating and introducing a decision aid based on the statistical model for use in primary care, including potential acceptability to primary care staff and patients.

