### **6.2 Setting**

Patient screening, invitation, recruitment and consent together with collection of index test variables will take place in Primary Care. We plan that the reference test will take place in GP surgeries and/or secondary clinics within each Research Network hub, using portable equipment and performed by suitably qualified specialist research staff (e.g. Research Nurses).

The qualitative study and field-testing of the prototype decision aid will take place in volunteer GP practices identified from those participating in the main study.

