### 8.1 Inclusion /Exclusion criteria

Inclusion Criteria	Exclusion criteria

 
• Men aged 16 years and over.
 
• Men who present to their GP with a complaint of one or more bothersome lower urinary tract symptoms#
 
• Men able and willing to give informed consent for participation in study
 
• Men able and willing to undergo all index tests and reference test, and complete study documentation.
 
 
# This would include men on current treatment, but who are still symptomatic
	
 
• Men with neurological disease or injury affecting lower urinary tract function
 
• Men with LUTS considered secondary to current or past invasive treatment or radiotherapy for pelvic disease Men with other contraindications to urodynamics e.g. Heart valve or joint replacement surgery within the last 3 months, immunocompromised/immunosuppressed.
 
• Men with indwelling urinary catheters or who carry out intermittent self-catheterisation
 
• Men whose initial assessment suggests that clinical findings are suggestive of possible:               
 
○ prostate or bladder cancer*
 
○ recurrent or persistent symptomatic UTI**
 
○ renal impairment
 
○ retention
 
 
 
• Men unable to consent in English or Welsh where a suitable translator is not available. This is a multi-centre study based in primary care, and we cannot guarantee translation facilities at all sites
 
 
*According to standard NHS cancer pathways. If later deemed unlikely, then eligible for study participation.
 
**If UTI successfully treated but LUTS remain, then eligible for study.

	
>This is a multi-centre study based in primary care, and we cannot guarantee translation facilities at all sites.

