*PSA test – within the previous 6 months prior to baseline visit					
**Urodynamics – within the last 6 months (providing the data meets the Quality Control 3 – item checklist within our specification)					

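### The Table 2 footnote lets urodynamics from the last six months stand as the reference test on signal quality alone, with no anchor visit and no condition on treatment change or blinding

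*Protocol*

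**What the plan says.** Two footnotes stand under Table 2 in Section 11.2. The PSA footnote accepts a result "within the previous 6 months prior to baseline visit". The urodynamics footnote accepts a test "within the last 6 months (providing the data meets the Quality Control 3" and completes the proviso with the checklist. Section 11.2 lists the three items: zeroing, subtraction of abdominal pressure, and the starting detrusor pressure.

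Elsewhere the protocol describes a prospective study test. Section 6.1 states: "All men in the study will undergo urodynamics as the reference test for diagnostic accuracy". Section 6.2 has it done "using portable equipment and performed by suitably qualified specialist research staff". Section 11 sets Part B aside for it. Section 11.2 keeps the study nurse unaware of index results not needed for the procedure. Section 10.4 provides sampled review of the recordings.

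On who may enter, Section 4.2 says: "Urodynamics, the reference test, is routinely performed in secondary care". Section 8.1 takes "Men who present to their GP with a complaint of one or more bothersome lower urinary tract symptoms", adds "This would include men on current treatment, but who are still symptomatic", and has no exclusion for previous urodynamics or referral. Section 9.1 searches records back over six months. Section 16.5 includes every participant with reference test data in the analysis.

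**The concern.** A diagnostic accuracy study needs index and reference tests to describe the same man in the same state. The footnote secures only that the old trace is technically sound. A man tested months ago may have learned his diagnosis and started or changed treatment before he fills in the ICIQ and IPSS, keeps the diary, has his residual scanned and uses the home flowmeter. The model would then be trained, and its sensitivity and specificity estimated, on index values that treatment or knowledge of the diagnosis may have altered, set against a reference result from before those changes.

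There is also a question of spectrum. The aid is meant for men at the point of GP presentation. A man with a recent urodynamic result has ordinarily already been referred, so he belongs to a later stage of the pathway.

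**Working it through.** **1. What the footnote permits.** It does not use the word replace, so substitution is an inference. It could be read as a window for the study's own test, but it looks backward from an unstated date and makes acceptance depend on whether the data pass a check. That fits a recording already made, as does its place beside a PSA footnote that plainly accepts an earlier result.

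**2. The texts side by side.**

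| Feature | Study test | Test accepted under the footnote |
|---|---|---|
| Who has it | All men (6.1) | Not those with an acceptable earlier test |
| Operator and review | Trained research staff, sampled review (6.2, 10.4, 11.1) | Not stated |
| Knowledge of index results | Restricted (11.2) | No condition |
| Timing | Part B, same day as Part A or a separate visit (11) | Last six months, no anchor |
| Treatment since the test | Little time for change | No condition |
| Entry to analysis | Yes (16.5) | Yes (16.5) |

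The PSA footnote counts from the baseline visit and this one counts from nothing. If the six months ran back from consent, the interval to later measurements such as home flow could exceed six months.

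**3. Which index tests are affected.** Examination, DRE and PSA come from the GP consultation, and the PSA may itself be old. The gap chiefly touches the questionnaires, frequency volume chart, post void residual and home uroflowmetry.

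**4. The plan's own counts.** Using the prevalences in Section 4 and the validation cohort of 325 in Section 16.1:
- DU: 325 × 0.16 = 52
- BOO: 325 × 0.31 = 100.75, about 101
- DO: 325 × 0.57 = 185.25, about 185

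These agree with Section 16.1.

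**5. Headcounts.** The protocol gives no share *f* of men with an earlier test. Assume *f* from 5% to 20%:
- 675 × 0.05 = 33.75; 675 × 0.20 = 135
- DU validation cases: 52 × 0.05 = 2.6; 52 × 0.20 = 10.4

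**6. Illustration of bias.** Assume also that a proportion *d* of these men have changed status by the time of the index tests, equally in either direction, and that true sensitivity and specificity are both 75%. Put e = f × d and let p be prevalence. Then

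apparent sensitivity = [0.75·p·(1−e) + 0.25·(1−p)·e] / [p·(1−e) + (1−p)·e]

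For DU with f = 10% and d = 10%, e = 0.01: (0.1188 + 0.0021) / (0.1584 + 0.0084) = 0.1209 / 0.1668 = 72.5%.

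| f | d | DU | BOO | DO |
|---|---|---|---|---|
| 5% | 10% | 73.7% | 74.4% | 74.8% |
| 10% | 10% | 72.5% | 73.9% | 74.6% |
| 10% | 20% | 70.2% | 72.8% | 74.2% |
| 20% | 20% | 66.0% | 70.8% | 73.5% |

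Apparent specificity stays at 74.6% or above for DU and 74.1% or above for BOO, and falls to 72.4% at worst for DO. The largest shift, 75 − 66.0 = 9.0 points for DU sensitivity, lies inside the 14-point lower margin that Section 16.1 allows. Sampling error would therefore not reveal it, and a larger sample would not remove it. The last row sets both assumptions at their extremes. The illustration leaves out any effect of known diagnosis on symptom reporting, which could raise apparent accuracy, so the net direction is open.

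**The case against.** The strongest reply is that the footnote may cover very few men and spares them a second invasive test, for which Section 4.2 gives a 5% infection risk. Treatment and medication history are already recorded (Table 2, Section 9.4), and the three-item checklist is in the minimum dataset. Home uroflowmetry follows urodynamics for every participant, so some index testing after the reference test is part of the design. An outside reader also cannot have seen study index results that did not yet exist. All of this stands and limits the size of the problem. It does not supply an anchor or a condition on interim treatment. It does not control what the outside reader knew from clinic work-up, or what the man knew when he completed the questionnaires.

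Four stronger readings are tempting but unsupported:

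- *Such men count as already referred and inflate the referral rate by a definite amount.* Sections 5.2 and 11.3 count decisions made after the GP has considered the study's results. A referral before entry is not one of these, and a man already under urology might be less likely to be referred again.
- *A hospital test contradicts the setting.* Section 6.1 does speak of "the invasive reference test (urodynamics) in community settings", but Sections 6.2 and 9.1 allow urodynamics in secondary care. The conflict lies in timing, treatment and blinding, not location.
- *These men would miss residual and flowmetry.* Table 2 gives both their own entries, without the footnote mark, and Section 8.1 requires willingness to undergo all index tests. What remains is a gap in wording: Part B is described around urodynamics, and flowmeter use is triggered by the call three days after it.
- *The footnote should simply be deleted.* That means repeating the test or losing the man, a trade-off for the sponsor.

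**Conclusion.** The point holds as a design weakness and an internal conflict. As written, the plan can pair an old reference result with later questionnaires, diary, residual and flow, and Section 16.5 carries every such pair into development and validation. The risks are bias in the accuracy estimates and a shift in case mix toward men already investigated.

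The size cannot be computed from the protocol. The headcounts and the illustrative fall in DU sensitivity (to between 73.7% and 66.0%) rest on shares and rates of change that the protocol does not give; they show that DU, the rarest diagnosis, is most exposed, and they are not estimates. If few men use the footnote, the bias is small and so is the cost of setting them aside.

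For the referral outcome, only this can be said: the CPRD comparator in Section 14.4 is built from incident presentations, with no LUTS code in the preceding 365 days and referral counted within 28 days. Men investigated in secondary care before entry do not match it.

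**What to change.** - Reconcile Sections 6.1, 11 (Part B), 11.2 (blinding), the Table 2 footnote and 16.5, so that the protocol says in one voice whether a pre-study test may serve as the reference standard.
- If it may, anchor the window to a named visit, as the PSA footnote does.
- Record the date of any earlier test and any change in LUTS treatment since.
- Exclude men with a pre-study reference test from the primary development and validation analyses and include them in a sensitivity analysis. Amend Section 16.5 to match.
- State that residual and home flowmetry are still collected from these men, and what starts the flowmetry when there is no post-urodynamics call.
- Report them separately in the comparison with CPRD.

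The cost is a short amendment to several sections, confirmation that the CRF (not shown) captures the two items, and the loss of some men, probably few, from the primary analysis. Those men would have to be made up within the planned 880 if 675 complete datasets are still required.

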### **11.3 Follow-up**

The participants will be followed up at approximately 3-6 months after their second visit (following the urodynamics reference test). Follow up will ascertain the management decisions that have been made by the GP after considering results and recommendations from the index and reference tests.

As a minimum requirement, we will collect the decisions regarding medical treatment and referral rates. We will also collect information regarding any study specific adverse events that have been experienced, as well as ensuring that all serious adverse events have been captured and reported.

A review of medical notes will be done by the research nurses to establish and report decisions in relation to advice and recommendations given to the patient regarding things like lifestyle changes.

## **12 Withdrawal & Loss to Follow-Up**

### **12.1 Withdrawal**

Participants have the right to withdraw consent for participation in any aspect of the study at any time. The participants care will not be affected at any time by declining to participate or withdrawing from the study.

If a participant initially consents but subsequently withdraws from the study, clear distinction must be made as to what aspect of the study the participant is withdrawing from. These aspects could be:

1. Withdrawal from index tests / reference test
2. Withdrawal from NHS medical note review
3. Withdrawal of Consent to all of the above

The withdrawal of participant consent shall not affect the study activities already carried out and the use of data collected prior to participant withdrawal. The use of the data collected prior to withdrawal of consent is based on informed consent before its withdrawal.

Furthermore, it is important to collect safety data ongoing at the time of withdrawal, especially if the participant withdraws because of a safety event. There is specific guidance on this contained in the Participant Information Sheet but briefly:

If a participant wishes to stop taking part in the study completely, they may need to be seen one last time for an assessment.

A participant may withdraw or be withdrawn from the study for the following reasons:

- Withdrawal of consent for investigation by the participant

- Any alteration in the participant's condition which justifies the discontinuation of the intervention in the Investigator's opinion
- Non-compliance

In all instances participants who consent and subsequently withdraw should complete a withdrawal form (see Withdrawal Form in study pack) or the withdrawal form should be completed on the participant's behalf by the researcher/clinician based on information provided by the participant. This withdrawal form should be sent to the Study Manager. Any queries relating to potential withdrawal of a participant should be forwarded to Study Manager.

## **12.2 Loss to follow up**

It is essential for the study that every man recruited completes all the assessments, particularly the urodynamic reference assessment. We will make every effort to ensure that each participant completes the assessments by emphasising the importance of obtaining a full data set (including urodynamic assessments). We will also arrange to complete the assessments at a time that is convenient to them so they will not have to travel far. At enrolment patients will be asked to provide contact details for members of the research team to contact while attempting to make assessment appointments. Participants will also consent to the research team communicating with their GP.

- Participants will be identified as lost to follow-up if it is not possible to contact them directly or via their GP for 6 weeks post consent.

## **13 Internal Pilot and Progression Criteria**

We will conduct an internal pilot phase over the first six - nine months of the recruitment phase (study months 6 – 15) (see criteria in Table 3 below).

The internal pilot phase will assess the site and patient recruitment rate, proportion of patients undergoing urodynamic assessments and those with a complete data set for analysis. The progression criteria have been designed to allow for mitigating strategies to be discussed to allow for some adaptation to recruitment processes. We will discuss the results with our Study Steering Committee, before reporting to the NIHR HTA Programme at Month 15, for permission to proceed.

In accordance with the HTA guidance on internal pilot studies, we will exclude the first two months of recruitment from our calculation of the recruitment rate as we anticipate a 'lag phase' during which practices are still being registered and participating clinicians develop confidence and competence in recruiting patients. We will constantly be assessing the criteria during the internal phase. We will also

conduct a qualitative evaluation of the acceptability of the gold standard urodynamic assessment with patients, and feedback from these interviews will assist with any refinement in processes during the pilot phase. We will also assess the prevalence of the three urodynamic diagnoses, this will ensure that we have powered the study correctly.

**Table 3: Progression Criteria**

[figure not shown]
Criteria	Level	Action
Site Recruitment	30 sites open	Monitor site recruitment and time to first recruit. At least 0.3 patients per practice per month.  Discuss potential mitigating strategies
Recruitment rate*	70 %  40 – 70%  < 40%	GO  Discuss potential mitigating strategies  STOP?
Gold standard undertaking (and evaluable?)	70 %  50 – 70%  <50%	GO  Discuss potential mitigating strategies  STOP?
Acceptability of gold standard urodynamic assessment	Qualitative interviews	

*\*Allowing for 2 –month lag phase*

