To complete the study we require 675 complete data sets. We plan to screen 3520 men with an expected 25% (880 men) agreeing to take part. This allows an attrition rate of a further 20-25% of these to achieve 675 complete datasets; 350 in the development cohort and 325 in the validation cohort.

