## **26 Milestones**

Month 1-6 = Study Set Up

Month 7-12 = Patient Recruitment and Follow Up (including 6 month Pilot and Acceptability Phase)

Month 19-24 = Results and Analysis

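### The pilot gives GO at 70% reference-test completion, but the sample size needs 76.7% (675 of 880), and the upper end of the stated attrition range also misses 675

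*Protocol*

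**What the plan says.** Protocol section 16.1 sets the target: "To complete the study we require 675 complete data sets", made up of 350 for development and 325 for validation. It then gives the route to it: "We plan to screen 3520 men with an expected 25% (880 men) agreeing to take part", followed by "This allows an attrition rate of a further 20-25% of these to achieve 675 complete datasets".

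Section 13, Table 3 sets the pilot levels. The row headed "Gold standard undertaking (and evaluable" (the parenthesis closes on a question mark) reads GO at 70%, discussion of mitigating strategies at 50-70%, and a queried STOP below 50%. The row headed "Recruitment rate" reads GO at 70%, discussion at 40-70%, and a queried STOP below 40%, after a two-month lag. The site row names 30 open sites and "At least 0.3 patients per practice per month", with monitoring and discussion of mitigation as its actions. That row has no GO level.

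Section 16.5 limits the analysis to men with reference test data. Section 12.2 treats completion of the urodynamic assessment as essential. Section 13 says that the pilot will also look at the proportion of men with a complete data set, but Table 3 has no row for it.

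**The concern.** The pilot assessment is the route by which section 16.4 allows the study to end early. Its levels should therefore be readable against the sample size. The reference-test row is not: a completion proportion below the one that section 16.1 relies on is labelled GO, and the table then asks for no discussion.

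Men without a reference test cannot make up the gap, because section 16.5 excludes them. The open query about evaluability adds to the problem. If the 70% counts tests done rather than tests that can be evaluated, the number of usable sets is lower still.

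At stake are the number of DU events available to the development model and the width of the interval for DU sensitivity. DU is the rarest of the three conditions and so the one that limits the design.

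**Working it through.** **Inputs.** 675 complete sets (350 + 325), 880 recruits and 20-25% attrition come from section 16.1. So do DU prevalence 16%, 5 events per variable, and an assumed sensitivity of 75%. The 70% levels come from Table 3. The average of 37 recruits per month is in section 13.1, and the pilot length of six to nine months is in section 13.

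**The plan's own figures.**
- 3520 × 0.25 = 880, as stated.
- 675 / (1 − 0.20) = 844 and 675 / (1 − 0.25) = 900. The planned 880 lies between them.
- Implied attrition: 1 − 675/880 = 23.3%, so required completion is 76.7%.

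**Ends of the attrition range, applied to 880.**
- 20%: 880 × 0.80 = 704, which meets 675.
- 25%: 880 × 0.75 = 660, which is 15 short.

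**Reference-test GO level, if sustained.**
- 880 × 0.70 = 616. Shortfall 675 − 616 = 59, and 59/675 = 8.7%.
- 616 is an upper bound on complete sets, because index tests can also be missing.
- Keeping 70% would need 675/0.70 = 964.3, so 965 recruits.

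**Consequence at 616 sets, split in the planned ratio.**
- Development: 616 × 350/675 ≈ 319. DU events: 319 × 0.16 ≈ 51, against 350 × 0.16 = 56. At 5 events per variable this supports 51/5 ≈ 10 parameters, against 56/5 ≈ 11.
- Validation: 616 × 325/675 ≈ 297. DU cases: 297 × 0.16 ≈ 48, against 52.
- Exact (Clopper-Pearson) 95% lower limit for an observed 75%: 13.9 points below at 52 cases, which reproduces the stated 14%, and 14.6 points below at 48 cases.

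**How recoverable a 70% pilot is.** Suppose the pilot holds n men at 70% and the rest complete at proportion c. Then 675 needs c = (675 − 0.70n) / (880 − n).
- n = 100: (675 − 70)/780 = 77.6%.
- n = 222 (6 × 37): (675 − 155.4)/658 = 79.0%.
- n = 333 (9 × 37): (675 − 233.1)/547 = 80.8%.

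The last two use the average rate. They probably overstate n, because section 13.1 plans lower accrual early on. They still show that later completion would have to exceed 76.7%, by more the larger the pilot.

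**Recruitment-rate GO level, if sustained.** Taking the 70% as a share of planned accrual, 880 × 0.70 = 616 recruits, which is below 675 before any attrition.

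**The case against.** The strongest reply is that a pilot GO level is a feasibility tolerance and not a forecast. Section 13 says that the criteria were designed with mitigation in mind and will be assessed constantly. Section 10.4 puts the heaviest checking of urodynamic tests at the start, with retraining where needed. Section 13.1 plans lower accrual early and higher accrual later. Results go to the steering committee and the funder, and the pilot also checks the prevalence of the three diagnoses. This stands to the extent that 70% in the pilot does not establish a final shortfall. It does not explain why a value below the required average should be the one that calls for no discussion.

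Three stronger readings are tempting, and the protocol does not support them.

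- **That a GO guarantees failure.** Every shortfall above holds only if the pilot value persists. For recruitment the plan is explicitly for a rise, and the monthly target curve is in a figure that is not shown, so the 70% cannot be traced month by month.
- **That 0.3 men per practice per month is another GO level set too low.** It is a monitoring floor with mitigation attached. Held for 24 months in 100 practices it gives 0.3 × 100 × 24 = 720 recruits. That is below 880, but it falls below 675 complete sets only once attrition is applied. The average that 880 needs, 880/2400 = 0.37, would be unsuitable as a pilot floor, because a study on its planned slow start could fail it.
- **That the study could end with 431 sets.** 880 × 0.70 × 0.70 = 431 requires both 70% levels to persist to the end with no response.

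The attrition range may also be defended as rounded: 23.3% lies inside it, and the gap at 25% is 15 men, or 2%. That is fair as to size, but the sentence still says that the range achieves 675, and its upper end does not.

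**Conclusion.** The mismatch is real and rests on the protocol's own figures. The GO level for the reference test is 70%, the sample size needs 76.7%, and the row does not settle what is counted. If 70% persisted and all 880 men were recruited, at most 616 sets would result. That is 59 (8.7%) short, with about 51 rather than 56 DU development events and a DU sensitivity lower limit about 15 rather than 14 points below 75%. This assumes 16% DU prevalence and the planned split between cohorts.

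The statistical loss at 616 is modest. The case for changing the table is that its threshold disagrees with the stated target and is cheap to correct. The 70% recruitment level is a weaker second instance: it would give 616 recruits only if held to the end, and accrual is planned to rise after the pilot.

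A separate inconsistency concerns timing. Section 26 gives "Month 7-12 = Patient Recruitment and Follow Up (including 6 month Pilot and Acceptability Phase" (closing parenthesis omitted here) and places results in months 19-24. The synopsis gives 24 months of recruitment, and section 13 has the study "before reporting to the NIHR HTA Programme at Month 15, for permission to proceed". On the section 26 list, recruitment would end before that decision. The list leaves months 13-18 blank, so it may simply be incomplete. It has no bearing on the GO levels.

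**What to change.** 1. In Table 3, define the reference-test criterion as the proportion of consented men with an evaluable test and delete the question mark. Set GO at 77% or more (880 × 0.77 = 677.6) and make 50-77% the band for discussing mitigation.
2. Add a row for projected complete sets: projected recruits on the planned accrual curve multiplied by the evaluable proportion. GO at 675 or more; otherwise mitigation, or a restatement of the precision that can be reached. This row also deals with the recruitment-rate level, because it allows for the planned rise in accrual.
3. In section 16.1, change the attrition range to up to 23%. If 25% is to be kept, the recruitment target would have to be 900.
4. Leave 0.3 per practice per month as the monitoring floor.
5. Separately, reconcile the section 26 milestones with the 24-month recruitment in the synopsis and the month-15 decision in section 13.

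The cost is an edit to Table 3, one sentence in section 16.1 and the milestone list. The downside is that amber will be triggered somewhat more often, but amber only prompts discussion.
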